6. ADVERSE EVENTS

In the course of the clinical investigation, undesired medical events can occur in participating subjects, which are called adverse events (AEs). Furthermore, device deficiencies (DD) or complaints may also be observed. All AEs and device complaints of the investigational device shall be assessed by the investigator and shall be documented and reported throughout the clinical investigation.

The investigator shall submit to the sponsor all reportable events using the respective eCRFs provided within the EDC system.

Based on literature research, the adverse events listed in Appendix B may possibly occur as medical complications of a cardiac rhythm management system implant.

6.1 Definitions

6.1.1 Definition of Adverse Event

An AE is defined as any untoward medical occurrence, unintended disease or injury, or untoward clinical signs (including abnormal laboratory findings) in subjects, users or other persons whether or not related to the investigational medical device. This includes:

- Events related to the investigational medical device or the comparator
- Events related to the procedures involved
- For users or other persons, this definition is restricted to events related to the investigational medical devices.

6.1.2 Definition of Adverse Device Effect

An adverse device effect (ADE) is an AE that is related to the use of an investigational medical device. This includes any AE resulting from insufficient or inadequate instructions for use or the deployment, implantation, installation, or operation, or any malfunctioning of the investigational device and any event resulting from use error or from unintentional misuse of the investigational device.

Adverse events, which result from the required medical procedures involved, when implanting, using or testing the respective investigational device, even if not directly related to the device (e.g. anesthetic complications, wound healing disturbances, lead perforation, etc) are considered ADEs.

Three categories for classification of relationship to the investigational device and/or procedure are available:

- Clearly not related: A relationship of the AE to the investigational device and / or procedure can be excluded.

- Possibly related: It cannot be excluded that there is a connection with the device under investigation and / or the procedure.
- Clearly related: A relationship of the AE to the investigational device and/or procedure is likely/sure.

6.1.3 Definition of Unanticipated Adverse Device Effect

As defined in 21 CFR Part 812.3, an unanticipated adverse device effect is any serious adverse effect on health or safety or any life-threatening problem or death caused by, or associated with, a device, if that effect, problem or death was not previously identified in nature, severity or degree of incidence in the investigational plan or application (including a supplementary plan or application), or any other unanticipated serious problem associated with a device that relates to the rights, safety or welfare of subjects.

A listing of previously identified adverse events along with anticipated frequency is provided in Appendix B. It is important to note that random component failures or problems caused by misuse of the product are not considered unanticipated adverse device effects.

6.1.4 Serious AEs, ADEs, and UADEs

AEs, ADEs, and UADEs are classified as serious if one or more of the following consequences are fulfilled:

- led to death
- led to serious deterioration in the health of the subject, that either resulted in
 - a life-threatening illness or injury, or
 - a permanent impairment of a body structure or a body function, or
 - in-patient or prolonged hospitalization, or
 - medical or surgical intervention to prevent life-threatening illness or injury or permanent impairment to a body structure or a body function.
- led to fetal distress, fetal death or a congenital abnormality or birth defect.

Note: Planned hospitalization for a pre-existing condition, or a procedure required by the protocol, without serious deterioration in health, is not considered a serious adverse event.

In-patient hospitalization is defined as at least one overnight stay (change of date) in a hospital. Events for which subjects are hospitalized for less than 24 hours without change of date will not be documented as serious, unless one or more of the other seriousness criteria are fulfilled.

6.1.5 Definition of Device Complaint

Device complaint is defined as any written, electronic, or oral communication that alleges deficiencies related to the identity, quality, durability, reliability, safety,

effectiveness, or performance of a device after it is released for distribution [21 CFR 820 3(b)].

6.2 Reporting Adverse Events

The investigator shall report to the sponsor, by completing the appropriate eCRF, the following types of events:

- all adverse events related to or possibly related to
 - investigational device
 - implanted system
- any major adverse events related to procedures involved with implanting, using, or testing the investigational device (see examples in Section 6.3 and definitions in Appendix A: Definition of Terms)
- any adverse device effects, regardless of severity and including both previously reported and unanticipated adverse events
- (MPP Sub-Study Only, see Section 11.5.4) any cardiovascular hospitalizations and any other hospitalizations in which cardiovascular symptoms occur on or before the date of the 12-Month follow-up
- (MPP Sub-Study Only, see Section 11.5.4) all adverse events that require additional invasive intervention to resolve, specifically related to the MPP feature of the CRT-D. These adverse events include any software issues related to MPP programming for any adverse event that occurs while MPP is enabled and that may be attributed to the use of the MPP feature.

(Please note: Phrenic nerve stimulation is an expected event during left ventricular threshold testing. As the Sentus QP lead allows for measurements in up to 12 different vectors, phrenic nerve stimulation might be a common observation in this study. Therefore phrenic nerve stimulation during threshold testing is only considered a reportable adverse event if serious medical symptoms occur.

Events will be reported on an Adverse Event eCRF or a Device Complaint eCRF, as appropriate. Events should be reported as information is available, even if this results in an incomplete eCRF. The investigator must follow-up all ongoing reportable events either as long as the subject participates in the clinical investigation, the clinical investigation is terminated, or until the event has been resolved, whatever comes first.

The investigator must characterize each event by a single primary diagnosis. The primary diagnosis may describe an event consisting of several clinically recognizable features, symptoms or secondary diagnoses. Note: The observed symptoms and secondary diagnoses must be properly documented in the respective eCRF.

Multiple events may occur simultaneously in one subject. For each medically independent event with a primary diagnosis an individual report must be provided.

In addition, the action taken/treatment should also be provided with any supportive documentation available.

The investigator has to ensure that all relevant information is available. This also includes information from other parties (family, other hospitals, etc.).

If a patient dies during the clinical investigation, the investigator shall document the cause of death, circumstances and place of death. All actions taken, which were initiated to gain further information must be documented in writing and provided to BIOTRONIK, Inc.

Investigators are required to adhere to applicable regulations and reviewing IRB reporting requirements for adverse events.

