2.4.2 Post-Approval Analysis

The sample size required to evaluate primary hypotheses 3 was estimated using the following design criteria:

- Study design: non-randomized
- Test basis: exact binomial test
- Type I error, alpha: 2.5% (one-sided)
- Statistical power: 80%
- Expected complication-free rate through 5-years: 94.75%

- H_A: Complication-free rate through 5-years post-implant > 92.5%

Based on the above criteria, a total of 979 evaluable subjects assessed at 5 years would be required to accept the primary 5-year safety alternative hypothesis.

An adjustment of 11% per year is used in the sample size estimation for primary endpoint 3 to account for subjects that exit the clinical investigation prior to having a 5-year (60-month) evaluation. Reasons that subjects may exit the clinical investigation include withdrawal of consent, mortality, device explant, change in physician, or subject moving. Therefore, up to 1754 evaluable subjects ($=979/0.89^5$) will need to be enrolled to account for premature study terminations.

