3.5.3 Date of Study Termination

The expected study termination for all subjects should not be earlier than the 60 month follow-up visit.

For all early study terminations, the following rules apply:

- In case of withdrawal of consent, date of study termination is the date of withdrawal of consent.
- In case of subject death, the date of study termination is the date of death.
- If subject is lost to follow-up, date of termination is the date of last documented contact with the subject.
- If a Sentus QP implantation was planned but was never attempted, the date of termination is the date of decision not to implant.
- If a Sentus QP implantation was initiated but not completed and the Sentus QP did not come in contact with the subject, date of unsuccessful implantation is date of study termination.
- If an attempt to implant Sentus QP lead was made and lead came in contact with subject but implantation was ultimately not successful, date of study termination is date of unsuccessful implantation.
- If the Sentus QP is explanted and not replaced with another Sentus QP, the date of study termination is the date the lead is explanted.

Study related procedures and documentation should end at the day of study termination for the respective subject.

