5. STUDY OVERSIGHT

5.1 Clinical Events Committee

A Clinical Events Committee (CEC) consisting of at least 3 independent Electrophysiologists or Cardiologists (with CRT experience) will be established to review and adjudicate all protocol defined adverse events reported by the investigational sites related to:

1. Lead or generator adverse event resolved by surgical reposition, surgical explanation, surgical replacement, surgical abandonment, or if other lead-related surgery is performed
2. Adverse event related to clinical lead failure, electrical lead failure, or mechanical lead failure, regardless of action taken. This includes PNS resolved by electrical abandonment and disabled pacing
3. Any major implant procedure related event that meets the criteria of a serious adverse event
4. (MPP Sub-Study Only, see Section 11.3.4) MPP sub-study related events.

Protocol defined adverse events that do not meet these criteria for CEC adjudication (e.g. reprogramming pacing output due to high LV threshold without a suspected or confirmed lead failure) will be included in the clinical report based on site-reported information.

The CEC will be blinded to the investigational site and subject identity, and to minimize bias members will not participate as investigators. The CEC will create a study specific charter defining the adverse event adjudication process, specifically detailing review guidelines along with appropriate response timelines.

Adverse events meeting the criteria described above will be adjudicated by the Clinical Events Committee. The Clinical Events Committee (CEC) will have the responsibility to adjudicate the classification, category, seriousness, and resolution of each reported adverse event. In addition, the CEC will also indicate whether the adverse event is related, possibly related, not related, or has an unknown relation to the Sentus QP lead or Plexa ICD lead. The CEC will decide for each event on the inclusion to the primary endpoint 3 analysis according to the definition for endpoint 3 relevant adverse events as documented in Section 6.6.2.

The Clinical Events Committee is responsible for:

- Endpoint adjudication of adverse events meeting the criteria above
- Adjudication meetings, as needed, via telephone conference or face-to-face
- Final decision on inclusion of each adverse event in the primary endpoint 3 analysis according to the definition provided in Section 6.6.2.
- Regular reporting of adjudication results to the sponsor

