In addition, the following procedure-related adverse events will be included in the analysis of primary endpoint 1:

- Pneumothorax directly associated with the Sentus QP lead

- Cardiac perforation with or without tamponade caused by the Sentus QP lead
- Coronary sinus dissections directly caused by the Sentus QP lead (e.g., dissections caused by lead delivery device are excluded)

Finally, subject deaths resulting from a Sentus QP lead-related AE will be included in the primary endpoint analysis.

6.6.2 Adverse Events Included in Primary Endpoint 3

ADEs related to the Sentus QP lead and resolution combinations that will be analyzed as part of the primary endpoint 3 ($p_{\text{Complication}}^{\text{SentusQP}}$) are presented in Table 8. Combinations marked with an “X” will be included but are not limited to the primary endpoint 3 analysis. All Sentus QP related ADEs meeting the below criteria occurring after successful implantation until the 60-month post-implantation visit will be included.

Table 8: Adverse Event/Resolution Combinations for Primary Endpoint 3 Analysis

Resolution	Clinical lead failure	Electrical lead failure	High pacing threshold excluding events within 45 days of implant or lead revision	Extracardiac stimulation	Intermittent capture excluding events within 45 days of implant or lead revision	Lead dislodgement >45 days post-implant or lead revision	Lead impedance out of range, high	Lead impedance out of range, low	Lead undersensing	Lead-related thrombosis	Loss of sensing	Mechanical lead failure	No capture excluding events within 45 days of implant or lead revision
Lead surgically repositioned	X	X	X	X	X	X	X	X	X	X	X	X	X
Lead surgically explanted	X	X	X	X	X	X	X	X	X	X	X	X	X
Lead surgically replaced	X	X	X	X	X	X	X	X	X	X	X	X	X
Lead surgically abandoned	X	X	X	X	X	X	X	X	X	X	X	X	X
Other lead-related surgery performed	X	X	X	X	X	X	X	X	X	X	X	X	X
Lead pacing polarity or mode reprogrammed*		X										X	
Lead electrically abandoned and pacing disabled	X	X										X	
Lead use continued based on medical judgment	X	X										X	

*Adverse events resolved by reprogramming of pacing polarity or pacing mode are only included in primary endpoint 3 analysis in cases of electrical or mechanical lead failure. Other adverse events, such as extracardiac stimulation, which are resolved by reprogramming are excluded.

In addition, the following adverse events will be included in the analysis of primary endpoint 3:

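### A lead event that is open at a completer's exit and operated on afterwards can be counted as complication-free in primary endpoint 3; the gap is narrow, but it always favours the device

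*Combined protocol and SAP*

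**What the plan says.** All references are to the combined protocol and SAP.

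- **Follow-up of open events (6.2).** "The investigator must follow-up all ongoing reportable events either as long as the subject participates in the clinical investigation", or until the study is terminated or the event resolves. The earliest of the three applies.
- **Documentation after exit (3.5.3).** "Study related procedures and documentation should end at the day of study termination for the respective subject". Sections 3.4.8 and 3.5.3 put planned exit no earlier than the 60-month visit. They set no later date and describe no contact after exit.
- **Endpoint definition (6.6.2, Table 8).** The endpoint is built from "ADEs related to the Sentus QP lead and resolution combinations that will be analyzed as part of the primary endpoint 3", for events from implantation to the 60-month visit. Ten of the 13 event types are marked only in the five surgical rows: high threshold, extracardiac stimulation, intermittent capture, dislodgement, high impedance, low impedance, undersensing, thrombosis, loss of sensing and no capture. Clinical, electrical and mechanical lead failure also count with some non-surgical resolutions. No row covers an event that is still open.
- **Adjudication (5.1).** The CEC is to "adjudicate the classification, category, seriousness, and resolution of each reported adverse event". An event reaches it through lead- or generator-related surgery, as a clinical, electrical or mechanical lead failure, or as a serious implant-procedure event. Other events in the main study are reported from site data.
- **Analysis set (2.3.4).** Implanted subjects who completed the 60-month visit, tested exactly against 92.5%.

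**The concern.** For most event types the endpoint needs both an event and a surgical resolution, but data collection may stop before the resolution is known. Take a dislodgement found at the 60-month visit and revised some weeks later. Its onset lies inside the window and the subject is in the denominator. If the subject has exited, the surgery need not be recorded, the event need not reach the CEC, and no combination in Table 8 is met.

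The misclassification can go only one way, since it removes failures and never adds them. The test is single-arm against a fixed goal, so no comparator carries the same loss. Endpoint 1 is much less exposed, because subjects remain in the study after 6 months and later surgery is still recorded. At 60 months that protection ends.

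**Working it through.** **1. The plan's own figure (2.4.2).** Inputs: goal p0 = 0.925, expected rate p1 = 0.9475, one-sided alpha 0.025, power 80%.

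n = [(1.960·√(0.925·0.075) + 0.842·√(0.9475·0.0525)) / 0.0225]² = 978.85, so 979.

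979 / 0.89⁵ = 1753.2, so 1,754. Both stated figures reproduce.

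**2. The pass line.** Exact (Clopper-Pearson) lower bound of the two-sided 95% interval at n = 979:

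- 57 failures (922 free): 92.52%, pass.
- 58 failures (921 free): 92.41%, fail.

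With this rule, P(at most 57 failures) is 0.0236 at a true rate of 92.5% and 0.811 at 94.75%. Expected failures are 979 × 0.075 = 73.4 and 979 × 0.0525 = 51.4.

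**3. How many events could be open at exit.** The documents give no time from detection to surgery, so this step rests on assumptions: failures arise at a constant rate over 1,826 days, surgery follows detection by L days, the subject exits at the 60-month visit, and a share s of failures counts only through surgery. The hidden fraction is f = s × L / 1826. The expected number missed at the goal is 73.4 × f. The false-success probability is P(X ≤ 57) with X binomial(979, 0.075 × (1 − f)).

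| s | L (days) | f | Missed at 92.5% | Missed at 94.75% | False-success probability at 92.5% |
|---|---|---|---|---|---|
| 0.5 | 14 | 0.4% | 0.3 | 0.2 | 2.5% |
| 0.5 | 30 | 0.8% | 0.6 | 0.4 | 2.8% |
| 0.5 | 60 | 1.6% | 1.2 | 0.8 | 3.3% |
| 0.5 | 90 | 2.5% | 1.8 | 1.3 | 3.8% |
| 1 | 14 | 0.8% | 0.6 | 0.4 | 2.7% |
| 1 | 30 | 1.6% | 1.2 | 0.8 | 3.3% |
| 1 | 60 | 3.3% | 2.4 | 1.7 | 4.5% |
| 1 | 90 | 4.9% | 3.6 | 2.5 | 6.0% |

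With nothing hidden the figure is 2.4%.

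**4. Limits of the model.** If complications cluster early, fewer are open at exit and every row shrinks. Table 2 shows 2.87% of subjects with a complication by 6 months and Table 13 shows 2.4–2.6%, which points that way. Endpoint 3 leaves out some events in the first 45 days, so these rates do not carry over directly. The model also treats the full 7.5% as failures among 979 completers. Subjects explanted without a new Sentus QP lead leave the study (3.5.2.5) and hence the analysis set, so the table isolates this one gap and is not a full operating characteristic of the test.

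**The case against.** The strongest reply is that the documents never say such a subject is complication-free.

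- **Exit date.** The dated rules in 3.5.3 are for early terminations. For completers the 60-month visit is only the earliest exit, so a site may keep a subject with an open event in the study. This stands as a permission. Nothing requires it, and practice could differ by site.
- **Complete information.** Section 6.2 also asks for the action taken and for relevant information from other hospitals. It sets no period after exit, while the same section and 3.5.3 do set an end.
- **Classification.** Table 8 is not exhaustive and the CEC makes the final inclusion decision. An unresolved pacing or sensing problem may be classed as clinical lead failure, which counts without surgery. This narrows the gap. However, Appendix A requires that the problem persist despite reprogramming or repositioning, which a newly found problem awaiting revision may not meet. An open event outside the lead-failure categories also lacks the surgical route to the CEC.
- **Edge of the window.** Any endpoint defined by an intervention has a boundary at its horizon, and surgery after year 5 could be read as outside it. That is a defensible choice, but the plan dates events by occurrence up to the visit and does not say which date governs an open one.

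A reader might also infer a larger effect: that half of failures wait silently for a scheduled visit up to 183 days away. With a 45-day lag, 0.5 × 183/1826 + 0.5 × 45/1826 = 6.2% would be open under a uniform hazard, or about 3.9% if half of failures fall in year 1. Hidden shares of 6% and 4% give false-success probabilities of 7.2% and 5.1%. The documents do not support this. Acceptance of Home Monitoring is an inclusion criterion (3.1.3), its activation is recommended (3.2.4), and when active it reports LV threshold, sensing and impedance daily (2.5.4). That calculation also applies the open share to lead failures, procedure events and deaths, which can count without surgery.

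**Conclusion.** The point holds in a limited form. Read together, 6.2, 3.5.3, 5.1 and Table 8 allow a lead event with onset by the 60-month visit, in one of ten categories and operated on after exit, to be counted as complication-free. They do not make this certain for every such subject. It needs exit before the surgery and an event not classed as a lead failure.

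The effect is small and one-directional: about 0.3–3.6 missed events at the goal, about 0.2–2.5 at the expected rate, and a false-success probability of about 2.5–6.0% against 2.4% as designed. These ranges rest on the assumed constant hazard, the 14–90 day lag and the share of surgery-dependent failures. Early clustering lowers them. A single uncounted event changes the conclusion only when the count is at the 57/58 boundary. Because the rule is written into the plan, favours the device and is cheap to close, it should be changed before 60-month data accrue.

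**What to change.** - **6.2:** exempt events related or possibly related to the Sentus QP lead that are open at the 60-month visit from the rule that stops follow-up at the earliest of the three endings. Collect their resolution by record request up to a fixed data cut-off, and align the end-of-documentation sentence in 3.5.3.
- **6.6.2:** state that an event with onset on or before the 60-month visit is classified by its resolution at that cut-off.
- **5.1:** send Sentus QP lead events still open at the 60-month visit to the CEC.
- **Analysis:** add a sensitivity analysis for endpoint 3 that counts events still open at the cut-off as failures.

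The cost is a few sentences, record requests for the few subjects concerned, and possibly a slightly less favourable reported rate. The 979 evaluable and 1,754 enrolled subjects are unchanged.
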